## 6.2. Safety Endpoints

- 1. Echocardiography: at each visit and change from baseline
  - a. Interventricular septal thickness (mm)
  - b. Posterior left ventricular wall thickness (mm)
  - c. Left atrial diameter (mm)
  - d. Left atrial volume (cc)
  - e. Left ventricular end diastolic diameter (mm)
  - f. Left ventricular mass (g)
  - g. Ejection fraction (%)
  - h. Right ventricular wall thickness (mm)
- 2. Doppler data
  - a. E/A ratio
  - b. Mitral Deceleration time (msec)
- 3. Tissue Doppler
  - a. Septal s', e', a' (cm/sec)
  - b. Lateral s', e', a' (cm/sec)
  - c. Pericardial effusion (yes/no)
  - d. Valvular abnormalities (thickening, regurgitation)
- 4. Calculated Echo variables will include, but are not limited to:
  - a. Relative LV wall thickness (Post wall thickness X 2 divided by LVED)
  - b. LA Volume index (LA size/body surface area)
  - c. LV mass/voltage ratio (LV mass divided by largest voltage on ECG)
  - d. e:e' ratio
- 5. Select echocardiogram parameters will be categorized as indicated below:
  - a. Left ventricular posterior wall thickness  $\geq$  13 mm
  - b. Left ventricular septal thickness  $\geq$  13 mm

- c. Right ventricular thickness  $\geq$  7 mm
- d. E/A ratio  $\geq$  2
- e. E/Eprime Lateral  $>$  15
- f. E/Eprime Septal  $>$  15
- g. Ejection fraction  $<$  50%
- h. E deceleration time  $\leq$  150 msec
- i. Isovolumic relaxation time (IVRT)  $\leq$  70 msec
- j. Any valve thickening
- k. Abnormal respiratory variation of inferior vena cava
- l. Pericardial effusion

6. ECG values: at each visit and change from baseline

- a. PR interval (msec)
- b. RR interval (msec)
- c. QRS interval (msec)
- d. QT and QTc interval (msec)
- e. heart rate (bpm)
- f. overall interpretation, normal/ abnormal findings and clinical significance
- g. Corrected QTc will be calculated using Bazett's and Fridericia's correction formulas.
- h. QTc  $>$  450 msec
- i. QTc  $>$  480 msec
- j. QTc  $>$  500 msec
- k. Change in QTc between 30 msec (inclusive) and  $<$  60 msec
- l. Change in QTc  $\geq$  60 msec
- m. Change in QTc  $\geq$  90 msec

7. Clinical laboratory tests: at each visit and change from baseline

The following list of clinical laboratory endpoints was collected during the course of the study. However, the summary tables will be restricted to the measures indicated with an asterisk (\*). All measures will be included in the subject listings.

### **Hematology and Biochemistry**

- a. Alkaline phosphatase (ALP)\*
- b. Alanine aminotransferase (ALT)\*
- c. Aspartate aminotransferase (AST)\*
- d. amino-terminal B-type natriuretic peptide (NT-pro-BNP)\*
- e. Blood urea nitrogen (BUN)
- f. Gamma glutamyl transferase (GGT)\*
- g. Creatinine
- h. Total bilirubin\*
- i. International normalized ratio (INR)\*
- j. Troponin I\*
- k. Troponin T\*
- l. Prothrombin time\*
- m. Sodium
- n. Globulin

- o. Potassium
- p. Chloride
- q. Bicarbonate
- r. Cholesterol
- s. Calcium
- t. Uric acid
- u. Inorganic Phosphorous
- v. Thyroid-stimulating hormone
- w. Glucose
- x. Total thyroxine (T4)
- y. Free T4
- z. Total proteins
- aa. Prealbumin (transthyretin)
- bb. Hemoglobin
- cc. Platelets
- dd. Hematocrit
- ee. White blood cell count
- ff. Red blood cell count
- gg. Neutrophils
- hh. Lymphocytes
- ii. Mean corpuscular volume
- jj. Monocytes
- kk. Mean corpuscular hemoglobin
- ll. Eosinophils
- mm. Mean corpuscular hemoglobin concentration
- nn. Basophils
- oo. Retinol-binding protein

**Urinalysis**

- a. Bilirubin
- b. pH
- c. Blood (free Hb)
- d. Protein
- e. Nitrite
- f. Glucose
- g. Urobilinogen
- h. Ketones
- i. Specific gravity

**8. Mortality and hospitalization (all-cause and cardiac-related)**

All-cause of mortality is defined as any death occurring during the study. Cardiac-related mortality will be any mortality meeting the following MedDRA criterion: 1) AE body system (AEBODSYS) = "CARDIAC DISORDERS", or 2) AE preferred term (AEDECOD) in (CHEST DISCOMFORT, CHEST PAIN, DEATH, CEREBROVASCULAR ACCIDENT, EMBOLIC STROKE, DISEASE

PROGRESSION). Description on the time to mortality analysis can be found in [Section 8.1.3](#).

All cause of hospitalization is defined as any adverse event for which SAE type “3=Hospitalization” in the Adverse Event (AE) CRF. The cardiac-related hospitalization will be any hospitalization meeting the following MedDRA criterion:1) AE body system (AEBODSYS) = “CARDIAC DISORDERS”, or 2) AE preferred term (AEDECOD ) in (CHEST DISCOMFORT, CHEST PAIN, DEATH, CEREBROVASCULAR ACCIDENT, EMBOLIC STROKE, DISEASE PROGRESSION).

### **6.3. Physical exam and Medical history**

Physical exam will be listed by subject and visit in the listings. Medical history will be listed by subject.

### **6.4. Adverse Events**

Treatment emergent adverse events will be summarized by all causes and treatment relatedness groupings. Treatment emergent is defined as either a new adverse event or a worsening of an ongoing adverse event during the course of Study Fx1B-303 (B3461026). In addition, severity of the adverse events will be summarized by all causes and treatment relatedness.

### **6.5. Discontinuations**

All reasons for discontinuation will be summarized including: discontinuations due to adverse events, discontinuations due to laboratory abnormalities, discontinuations due to death, discontinuations due to liver and/or heart transplant and all cause discontinuation.

### **6.6. Covariates**

Due to the small number of subjects, lack of comparator group and the descriptive nature of this study, baseline will be used as a covariate in the change from baseline models and where appropriate, duration of disease will be used as a covariate.

### **6.7. Baseline**

Baseline will be defined for Fx1B-201 and B3461026, respectively. The baseline for Fx1B-201 will be defined as the last measurement prior to the first dose of study drug in Study Fx1B-201. The baseline for B3461026 will be defined as the measurement from the end of study visit of Study Fx1B-201, or from the Day 0 visit of Study B3461026, whichever comes later. Baseline for Fx1B-201 and for B3461026 will be summarized.

## 7. HANDLING OF MISSING VALUES

Data which are based on entire scales which are missing will be analyzed as follows:

If the data are time until event data and there is no observed event (at any point during the trial) the observation will be censored at the last observation. If there was an observed event, the data associated with the first observation of that event will be used; all other observations will not be needed.

For all other data types, the data will be analyzed as follows: for analyses at each visit, the missing observations will not be used. Any visit after the subject was discontinued will remain as missing data.

For any subject missing a 12-month visit observation from Study Fx1B-201, if the Day 0 visit observation from the Fx1B-303 study is reported, the Day 0 visit observation from the Fx1B-303 will be imputed for the 12-month visit observation for Study Fx1B-201.

For specific scoring details, see [Appendix 1](#).

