- Chronic use of non-protocol approved non-steroidal anti-inflammatory drugs (NSAIDs), defined as greater than 3 to 4 times/month. The following NSAIDs are allowed: acetylsalicylic acid, etodolac, ibuprofen, indomethacin, ketoprofen, nabumetone, naproxen, nimesulide, piroxicam, and sulindac.
- Patient has a clinically significant medical condition that, in the opinion of the Investigator, would place the patient at an increased risk to participate in the study.
- Pregnant females; breastfeeding females; females of childbearing potential.
- Patient has received a liver or heart transplant.

Study Design:

This is a Phase 3, open-label study designed to obtain additional long-term safety and efficacy data in patients who successfully completed Protocol Fx1B-201. These patients will be treated, with once daily 20 mg oral tafamidis (soft gelatin capsule) for up to 10 years from the date of enrollment in Protocol Fx1B-303, or until subject has access to tafamidis for TTR-CM via prescription. Upon regulatory approval for the treatment of TTR-CM in their respective country and access to prescription tafamidis, subjects may be withdrawn from the study. The decision to withdraw subjects to transition to commercial supply will be done in consultation between the investigator and the sponsor.

Subjects who successfully complete Fx1B-201 will report to the clinical unit on Day 0 to sign the informed consent form and determine eligibility for Protocol Fx1B-303. In addition, on Day 0, subjects will have their entrance criteria reviewed, and medical

histories and demographic characteristics obtained. The physical examination (including weight and vital signs) and the relevant end of study clinical laboratory tests (alkaline phosphatase, alanine aminotransferase, aspartate aminotransferase, blood urea nitrogen, gamma glutamyl transferase, creatinine, total bilirubin, international normalized ratio, troponin I, troponin T, and amino-terminal B-type natriuretic peptide) from Protocol Fx1B-201 will be used for Protocol Fx1B-303. If more than 30 days has elapsed between the final study visit of Protocol Fx1B-201 and Day 0 of Protocol Fx1B-303, an abbreviated physical examination (including weight and vital signs) and clinical laboratory assessments must be performed on Day 0.

Eligible subjects will begin once-daily dosing with 20 mg tafamidis at home on Day 1 (i.e., first dose) and will return to the clinical unit for study visits every 6 months.

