1.2.4. Tafamidis Clinical Experience

The clinical development program for tafamidis has included 13 controlled and uncontrolled clinical trials and two non-interventional, observational studies completed primarily in patients with TTR-FAP. As of 13 May 2011, patients with TTR-FAP (n=127) received 20 mg of tafamidis administered daily for an average of 538 days (range of 15 to 994 days) or approximately 187 patient-years. The mean duration of exposure was 17.7 months: 87 were treated for at least 1 year, 43 were treated for at least 2 years, and 31 were treated for at least 30-<36 months.

The tafamidis 20 mg soft gelatin capsule (as used in the clinical studies) demonstrated a half-life average of 59 hours and $C_{avg(ss)}$ average of 2.07 μ g/mL (SD=0.20). The tafamidis 20-mg soft gelatin capsule daily dose resulted in an average fluctuation (peak to trough) of

51.8%, with an average minimum concentration (C_{min}) of 1.61 μ g/mL and an average C_{max} of 2.66 μ g/mL. The average range was consistent with the 1 to 2 μ g/mL required to stabilize TTR levels beyond the upper limit of the normal range; steady state was attained within 12 days, and exposure was consistent across subjects, with low variability across subjects for key PK parameters. Note that steady-state exposure was similar between males and females. Therefore, the 20 mg daily dose has been used in the development program. Further, based on a population PK analysis, no dose adjustment is necessary for the elderly or patients with hepatic or renal impairment.

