4.1. Inclusion Criteria

Subject eligibility should be reviewed and documented by an appropriately qualified member of the investigator's study team before subjects are included in the study.

Subjects must meet all of the following inclusion criteria to be eligible for enrollment into the study:

- Evidence of a personally signed and dated informed consent document indicating that the subject (or a legal representative) has been informed of all pertinent aspects of the study.
- Male or female subjects with TTR-CM who have not undergone liver or heart transplantation and who have successfully completed Protocol Fx1B-201.
- Subject has successfully completed Protocol Fx1B-201.
- If female, subject is post-menopausal. If male, female partner is post-menopausal; or if female partner is of childbearing potential, then the subject is willing to use an acceptable method of birth control for the duration of the study and for at least three months after the last dose of study medication.

Note: The definition of acceptable method of birth control will be based on the judgement of the Investigator or designated associate.

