6.1. Screening/Baseline Assessment

The end of study physical examination (including weight and vital signs) and the relevant clinical laboratory assessments from Protocol Fx1B-201 will be used as the Day 0 assessments for Protocol Fx1B-303. If more than 30 days has elapsed between the final study visit of Protocol Fx1B-201 and Day 0 of Fx1B-303, an abbreviated physical examination (including weight and vital signs) and clinical laboratory assessments must be performed on Day 0.

Subjects will be required to sign an informed consent form before beginning participation in Protocol Fx1B-303. The following procedures will be performed on Day 0:

- All inclusion and exclusion criteria will be reviewed to ensure eligibility for participation in this study.
- Demographics (date of birth, age, gender, and race) for all subjects will be collected.
- A complete medical history will be obtained.
- Abbreviated physical exam including weight and vital signs (if not conducted within 30 days of Day 0).
- Collect blood/urine samples for clinical laboratory assessments (Section 7.3) (if not collected within 30 days of Day 0).
- Ask subjects non-leading questions such as “How do you feel?” and record adverse events.
- Record concomitant medications.
- Dispense 3 month supply of investigational product with instructions that subject is to administer the first dose at home on the following day as instructed (Section 5.2.3).

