### **Appendix 2. Definition and Use of Visit Windows in Reporting**

For the purpose of this study, Day 1 is defined as the first dose day under this protocol.

Day 1  $\pm$  1 week

Every other 3 month telephone visits between clinic visits  $\pm$  1 week

Clinic visits every 6 months  $\pm$  2 weeks

End of study visit  $\pm$  2 weeks

However, in order to maximize the use of all available data, the visit windows for each visit are expanded as follows:

Day 0: End of study visit from Fx1B-201

Day 1 + 1.5 months

Telephone contact (every 3 months between clinic visits)  $\pm$  1.5 months

Clinic visits (every 6 months)  $\pm$  3 months

End of study visit (see details below)

In the event that there is a break between the last visit of the parent study (Fx1B-201,) and the first day of dosing in the current study Fx1B-303 (B3461026); then the visit associated with the first day of enrollment in the current study Fx1B-303 (B3461026) will be the baseline visit of this study.

For an early termination visit within study B3461026 (Fx1B-303): The existing windowing rules will be used and as such, the data in the early termination visit should never replace an existing visit. If the visit covered by the windowing rules above is already populated with an existing visit, then the EOS visit should be mapped forward to the next clinic visit.

As an example, the EOS visit occurs at month 68.

If there is no month 66 visit, then the EOS visit becomes the month 66 visit.

If there is a month 66 visit, then the EOS visit becomes the month 78 visit.

For an unscheduled visit:

If possible, the existing windowing rules will be used, but the data should never replace an existing visit. If the visit is already populated, then the unscheduled visit should be mapped forward to the next appropriate visit for that measure if that visit is available.

As an example, the unscheduled visit occurs at month 68 and the data are collected annually.

If there is no month 66 visit, then the unscheduled visit becomes the month 66 visit.

If there is a month 66 visit, but no month 78 visit then the unscheduled visit becomes the month 78 visit.

If there are both month 66 and month 78 visits, then the unscheduled visit is not included in the summary analyses but is included in the listing as unscheduled.

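### SAP Section 7 fills a missing Fx1B-201 12-month value with the Fx1B-303 Day 0 value, with no limit on the interval and no on-drug condition

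*SAP*

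**What the plan says.** SAP Section 7 otherwise leaves a missing visit value missing. It makes one exception: for a subject without a 12-month observation from the parent study, "the Day 0 visit observation from the Fx1B-303 will be imputed for the 12-month visit observation for Study Fx1B-201". The only condition is "if the Day 0 visit observation from the Fx1B-303 study is reported".

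The protocol does not bound the time between the studies. Inclusion criterion: "Subject has successfully completed Protocol Fx1B-201", with no time limit since completion. Section 6.1 opens the longer-gap case with the words "If more than 30 days has elapsed between the final study visit of Protocol Fx1B-201 and Day 0 of Fx1B-303" and then calls for a new abbreviated examination and laboratory tests on Day 0. A longer gap leads to re-measurement, not exclusion. SAP Appendix 2 also provides for interrupted treatment: "In the event that there is a break between the last visit of the parent study" and the start of dosing in Fx1B-303, the enrolment visit becomes the baseline of the current study. No length is given for that break.

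Under Protocol Section 5.2.2, drug is dispensed on Day 0 and first taken on Day 1.

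**The concern.** The 12-month value is meant to describe a subject after 12 months of open-label tafamidis. A Day 0 value taken after a break is later than that and precedes the restart of drug. The rule lets it stand at month 12 all the same. Two things are at stake. The observation is misdated in the cumulative series, and an off-drug interval may be mixed into a point read as on-treatment. The biomarkers are the sensitive case, because Protocol Section 1.2.4 uses the 12-month NT-proBNP and troponin results to argue that cardiac status held steady on tafamidis.

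SAP Section 6.7 also takes the later of the Fx1B-201 end-of-study value and the Day 0 value as the B3461026 baseline. One measurement could then close the parent study and open the extension, although a break lies between the two.

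**Working it through.** The plan states no figure for this rule, so there is nothing to reproduce. The check sets the relevant places side by side and then does three small calculations.

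**1. Is there a limit anywhere?**

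| Place | What it governs | Limits the substitution? |
|---|---|---|
| SAP 7 | Filling the missing 12-month value | No; Day 0 need only be reported |
| Protocol 4.1, 4.2 | Entry | No; completion of Fx1B-201 only |
| Protocol 6.1 (30 days) | When Day 0 tests must be done anew | No; a trigger for measurement |
| SAP Appendix 2 (±3 months for clinic visits) | Fx1B-303 visit windows | No; not applied to this rule |

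**2. Which measures?** The Day 0 procedures in Protocol 6.1 and the Schedule of Activities are laboratory tests (including NT-proBNP and troponin I and T), an abbreviated examination, weight and vital signs. Patient Global Assessment, NYHA class, KCCQ, walk test, echocardiogram and ECG are not scheduled on Day 0. Of the laboratory tests, SAP 6.2 summarises only the starred ones; creatinine, BUN and electrolytes, for example, are only listed.

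**3. Where does the value enter?** SAP 8.1.1 takes change from the Fx1B-201 baseline, so the substituted value is a post-baseline point at month 12. It does not alter the reference for later changes from that baseline.

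**4. Timing.** Assume the final Fx1B-201 visit was at month 12. Actual month = 12 + gap in days / 30.4375.

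- 30 days: 13.0
- 60 days: 14.0
- 90 days: 15.0
- 180 days: 17.9

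All would be labelled month 12.

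**5. Drug level, if dosing stopped at the last Fx1B-201 visit.** This is an assumption. Protocol 1.2.4 says the capsule "demonstrated a half-life average of 59 hours", with average, minimum and maximum steady-state levels of 2.07, 1.61 and 2.66 µg/mL and a stabilising range of 1 to 2 µg/mL. Assuming first-order decay, days to reach 1 µg/mL = 59 × log2(C/1) / 24.

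- From 2.07: 59 × 1.05 / 24 = 2.6 days
- From 1.61: 1.7 days
- From 2.66: 3.5 days

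With the lower ex vivo bound of 0.7 µg/mL in Protocol 1.2.1, the times are 3.0 days (from 1.61) to 4.7 days (from 2.66). At 30 days, 720 / 59 = 12.2 half-lives have passed and 0.5^12.2 = 0.0002 remains, about 0.02%.

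**6. Weight of one subject.** Protocol 1.2.4 gives 35 subjects in Fx1B-201 and 2 deaths by 12 months, so at most 33 could contribute. One subject is 1/33 = 3.0%. If one assumes 1 to 5 imputed values, the share is 3.0% to 5/33 = 15.2%.

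**The case against.** The case against is substantial, and several stronger readings fail.

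- **A reader might infer that the values available for imputation come mainly from subjects with long gaps.** They need not. The rule acts only when the 12-month value is missing. The procedure list in Protocol 6.1 asks for a Day 0 laboratory sample "if not collected within 30 days of Day 0", and its item for examination and vital signs works the same way. A subject who missed the month-12 measurement is therefore measured on Day 0 whether the gap is one day or a hundred. A subject re-measured only because of a long gap, who has a 12-month value, triggers no imputation.
- **A reader might infer that SAP 7 contradicts the protocol's 30 days.** It does not. That figure decides when parent-study results may stand in for Day 0. It does not say which values may represent month 12. The SAP's own reporting tolerance for Fx1B-303 clinic visits is ±3 months, and a value up to about 90 days late would fit a window of that width.
- **A reader might infer that these subjects were off drug.** The documents do not say so. The break in Appendix 2 is conditional, SAP Section 2 speaks of dosing continuing, and the Fx1B-201 protocol is not to hand. Being off drug is an inference from the foreseen break, the Day 1 first dose and the absence of any described bridging supply.
- **A reader might take the washout figures as a measure of bias.** They describe plasma level only. The documents give no withdrawal effect for any endpoint and call the disease slowly progressing.

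Appendix 2 also lists Day 0 as the Fx1B-201 end-of-study visit. Where the two coincide, the rule adds nothing; it matters only when Day 0 is a separate measurement. What remains is that the rule has no limit, and nothing in the objections supplies one.

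**Conclusion.** The point holds in a limited form. As written, SAP 7 permits a Day 0 value at any interval, taken before drug is restarted, to be analysed as the 12-month result, and the same value would also be the B3461026 baseline. This rests on two features of the documents: gaps over 30 days are allowed, and a break is foreseen. It does not show that any subject had such a gap and also lacked a 12-month value.

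Reach is confined to biomarkers, other laboratory tests, weight and vital signs. The number affected is unknown and the direction and size of any bias cannot be derived. The study is descriptive, with no hypothesis tests. Importance is low to moderate: worth correcting because the correction is simple, not because a result is known to be wrong.

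If dosing did stop at the last Fx1B-201 visit, levels would fall below the stated range within days. A cap on the interval alone, even at 30 days, would therefore not secure an on-drug value.

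**What to change.** In SAP Section 7, allow the substitution only when both conditions hold:

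1. There was no dosing break between the last Fx1B-201 visit and Day 0, with the SAP stating how a break is determined from the dosing records.
2. Day 0 falls within a stated maximum interval of the 12-month due date. The protocol's 30 days is one candidate; the SAP's 3-month clinic window would be the outer limit. The choice is a judgement, but it should be written down.

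Otherwise leave the 12-month value missing and use Day 0 only as the B3461026 baseline. Flag each imputed value in the listings with its gap length.

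The cost is a short addition to the SAP and possibly a few more missing 12-month values, which the repeated-measures model in SAP 8.1.1 can accommodate. No study procedure changes.
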